2.1.2. Safety data

Study period	Treatment groups	Analysis populations	Imputation method
“Chapter 1”: Period 1, up to Week 12	
The 4 original groups:
 
 – Placebo – GLPG0634 50 mg q.d. – GLPG0634 100 mg q.d. – GLPG0634 200 mg q.d. 	
Safety: all subjects randomized and exposed at least once.
	
Observed-case only (no imputation)

“Chapter 2”: Periods 1+2 together (full 24 weeks period)	
The 5 groups of the second study period, taking into account treatment switches:
 
 – Placebo switched to 100 mg q.d. – GLPG0634 50 mg q.d. increased to 100 mg q.d. – GLPG0634 50 mg q.d. continued – GLPG0634 100 mg q.d. continued – GLPG0634 200 mg q.d. continued 
For the subjects in the placebo and low dose group who discontinued prior to Week 12: they will be included in the “placebo switched to 100 mg q.d.” and “continued 50 q.d.” groups, respectively.
 
Note that AEs will be presented overall, but also split up in the two study periods.
	
Safety: all subjects randomized and exposed at least once during the study.
	
Observed-case only (no imputation)

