2.4.2. Totals across Groups

A total across all groups will be presented for the General (subject disposition, demographics, etc) part of the analysis. For the Safety parts of the analysis, a total across all GLPG0634 groups will be presented for data up to and including Week 12, and for data after Week 12 or data across the entire 24 weeks of the study a total across all groups will be presented. No totals will be presented for PD or Efficacy. Totals will only be shown on tables, but not on listings or figures.

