12.1.5. Calculation of Percentages

All percentages will be calculated against the total number of subjects that are still in the study in that particular analysis period.

12.1.6. Tables up to Week 12

No formal inferential statistics (p-values) will be derived.

An as-treated analysis will be performed. All tabulations and listings will present treatments rather than analysis periods.

Table 14.3.1.1: Treatment-emergent adverse events up to Week 12: Summary table

Tabulation per treatment of the number and percentage of subjects with the following:

- Subjects with at least one treatment-emergent adverse event (TEAE)
- Subjects with at least one serious TEAE
- Subjects who died (treatment-emergent)
- Subjects with at least one mild TEAE as worst intensity
- Subjects with at least one moderate TEAE as worst intensity
- Subjects with at least one severe TEAE
- Subjects with at least one TEAE that was considered treatment-related
- Subjects with at least one treatment-emergent SAE that was considered treatment-related
- Subjects with at least one TEAE for which the study treatment was temporarily stopped
- Subjects with at least one TEAE for which the study treatment was permanently stopped
- Subjects with at least one TEAE flagged as an individual stopping criterion by the investigator.

Population: safety.

Table to be created for the Week 12 interim analysis as well.

Table 14.3.1.2: Treatment-emergent adverse events up to Week 12: Summary table by region

Same table as the preceding one, but by geographical region.

Population: safety.

Table 14.3.1.3: Treatment-emergent adverse events up to Week 12: Tabulation of all adverse events

Tabulation of TEAE preferred terms per body class, per treatment group.

Population: safety.

Table to be created for the Week 12 interim analysis as well.

Table 14.3.1.4: Treatment-emergent adverse events up to Week 12: Tabulation of all adverse events by region

Same as previous table, but split up by geographical region.

Population: safety.

Table 14.3.1.5: Treatment-emergent adverse events up to Week 12: Tabulation of all adverse events by gender

Same as previous table, but split up for males and females.

Population: safety.

Table 14.3.1.6: Treatment-emergent adverse events up to Week 12: Tabulation of all adverse events by age category

Same as previous table, but split up for age categories:

< 45 ;

[45,65[;

[65,75[;

≥ 75 years.

Population: safety.

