12.1.7. Tables over the whole 24 weeks period

The same tables will be created for the full 24 weeks period of the study, using the 5 groups as specified in section 2.4.

All tables will be created for 3 analysis periods: “first 12 weeks”, “second 12 weeks”, and “full 24 weeks” as defined in section 3.2.

Population: Safety.

Table 14.3.1.16: Treatment-emergent adverse events over the whole study: Summary table

Tabulation per treatment of the number and percentage of subjects with the following:

- Subjects with at least one treatment-emergent adverse event (TEAE)
- Subjects with at least one serious TEAE
- Subjects who died (treatment-emergent)
- Subjects with at least one mild TEAE as worst intensity
- Subjects with at least one moderate TEAE as worst intensity
- Subjects with at least one severe TEAE
- Subjects with at least one TEAE that was considered treatment-related
- Subjects with at least one treatment-emergent SAE that was considered treatment-related
- Subjects with at least one TEAE for which the study treatment was temporarily stopped
- Subjects with at least one TEAE for which the study treatment was permanently stopped
- Subjects with at least one TEAE flagged as an individual stopping criterion by the investigator
- Subjects with at least one TEAE that has not resolved.

Population: safety.

Table 14.3.1.17: Treatment-emergent adverse events over the whole study: Summary table by region

(only for the “full 24 weeks”, not for the two periods separately)

Table 14.3.1.18: Treatment-emergent adverse events over the whole study: Tabulation of all adverse events

Table 14.3.1.19: Treatment-emergent adverse events over the whole study: Tabulation of all adverse events by region

(only for the “full 24 weeks”, not for the two periods separately)

Table 14.3.1.20: Treatment-emergent adverse events over the whole study: Tabulation of all adverse events by gender

(only for the “full 24 weeks”, not for the two periods separately)

Table 14.3.1.21: Treatment-emergent adverse events over the whole study: Tabulation of all adverse events by age category

(only for the “full 24 weeks”, not for the two periods separately)

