12.3.7. Analysis tables for the whole 24 weeks period

Repeat tables, population=safety, with the adapted treatment groups focusing on subjects who used GLPG0634 during both study periods:

Table 14.3.3.7: ECG over the whole study: Descriptive statistics of the actual values per time point**Table 14.3.3.8: ECG over the whole study: Descriptive statistics of the changes from baseline****Table 14.3.3.9: ECG over the whole study: Shift table of the QT abnormalities****Table 14.3.3.10: ECG over the whole study: Treatment-emergent QT abnormalities****Table 14.3.3.11: ECG over the whole study: Treatment-emergent abnormal change in QT****Table 14.3.3.12: ECG over the whole study: Frequency table of the eCRF ECG interpretation per time point**

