12.4.7. Tables over the whole 24 weeks period

The same tables again, but with adapted treatment groups focusing on the subjects who used GLPG0634 during both study periods. Time points to present: screening, baseline, Week 1-2-4-8-12, last on-treatment during period 1, worst case during period 1, Weeks 16-20-24, last on-treatment during period 2, last on-treatment during the whole study, follow-up (all follow-up visits in the study), worst case during period 2, worst case during the whole study.

Population: Safety.

Table 14.3.4.6: Vital signs over the whole study: Descriptive statistics of the actual values

Table 14.3.4.7: Vital signs over the whole study: Descriptive statistics of the changes from baseline

Table 14.3.4.8: Vital signs over the whole study: Summary table of means

Table 14.3.4.9: Vital signs over the whole study: Shift table of the abnormalities per time point

Table 14.3.4.10: Vital signs over the whole study: Treatment-emergent abnormalities per time point

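### The 24-week safety columns file early stoppers under treatments they did not continue or never took, and mix placebo time with GLPG0634 time; safety to Week 12 is reported cleanly

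*SAP*

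**What the plan says.** SAP 2.1.2 gives safety two analyses. Chapter 1 covers the period up to Week 12 in the four original arms. Chapter 2 covers the full 24 weeks in five columns defined by treatment sequence: placebo switched to 100 mg, 50 mg increased to 100 mg, 50 mg continued, 100 mg continued and 200 mg continued. SAP 4.5.2 confirms that the sequence defines the columns.

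For Chapter 2 the rule on early stoppers is: "For the subjects in the placebo and low dose group who discontinued prior to Week 12: they will be included in the" placebo-switched and 50-mg-continued groups, in that order. The next sentence adds: "Note that AEs will be presented overall, but also split up in the two study periods".

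- **Total column.** SAP 2.4.2 uses a GLPG0634-only total for safety up to Week 12, but "for data after Week 12 or data across the entire 24 weeks of the study a total across all groups will be presented".
- **AE periods.** SAP 12.1.7: "All tables will be created for 3 analysis periods" (first 12 weeks, second 12 weeks, full 24 weeks), in the five groups. The region, gender and age tables are the exception: they are made for the full 24 weeks and "not for the two periods separately". Under SAP 3.2 the full-24-weeks period starts at the first study drug intake, placebo included.
- **AE denominators.** SAP 12.1.5: "All percentages will be calculated against the total number of subjects that are still in the study in that particular analysis period".
- **Laboratory and vital signs.** SAP 12.2.8, 12.2.11, 12.4.5 and 12.4.7 add a whole-study worst case that takes all post-baseline values.
- **Group wording.** SAP 12.3.7 repeats the ECG tables "with the adapted treatment groups focusing on subjects who used GLPG0634 during both study periods". SAP 12.4.7 does the same for vital signs, "but with adapted treatment groups focusing on the subjects who used GLPG0634 during both study periods".

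**The concern.** A 50 mg subject has to reach Week 12 to be moved to 100 mg. Since every 50 mg early stopper is filed under *continued*, the *increased* column has no early discontinuations whatever the drug does, and *continued* carries all of them, together with the AEs those subjects had. Table 14.3.1.28 (AEs leading to discontinuation) is produced in these columns, including for the first 12 weeks. A reader comparing the two columns would see a difference that the column definition helps to produce.

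On the placebo side, subjects who never took 100 mg are counted in a column that names it. This sits badly with SAP 2.4.1, which wants safety problems assigned to the treatment actually used.

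Finally, full-24-week columns and totals that include 12 weeks of placebo can be mistaken for GLPG0634 incidence. No exposure-adjusted rate is planned that would separate the two.

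**Working it through.** The plan states no figure on this point, so there is none to reproduce. The only inputs from the documents are 70 subjects per arm and 280 in total (Protocol 8.5.4 and 8.8.2), and two 12-week periods. Dropout and switch rates are not given. Those below are assumptions and are shown as ranges.

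**1. Placebo share of treatment time, no dropout.**
- *Placebo switched* column: 70 × 12 / (70 × 24) = 840 / 1,680 = 50%.
- All-groups total: 70 × 12 / (280 × 24) = 840 / 6,720 = 12.5%.

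**2. The same with dropout.** Assume 5–15% of each arm stop before Week 12, at Week 6 on average, with no later dropout. At 10%, 7 stop and 63 remain in each arm:
- placebo time = 63 × 12 + 7 × 6 = 798 subject-weeks; time on 100 mg in that column = 63 × 12 = 756; share = 798 / 1,554 = 51.4%;
- the other three arms contribute 3 × (63 × 24 + 7 × 6) = 4,662; share of the total = 798 / (798 + 756 + 4,662) = 798 / 6,216 = 12.8%.

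Over 5–15% the shares are 50.7–52.0% and 12.7–13.0%, so dropout hardly matters here.

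**3. Make-up of the two 50 mg columns.** With *e* early stoppers and *s* switchers, *continued* holds 70 − *s* subjects, of whom *e* never continued.

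| Assumed stop / switch | *e* | *s* | Early stops in *continued* | In *increased* | Randomised arm |
|---|---|---|---|---|---|
| 5% / 30% | 4 | 20 | 4/50 = 8.0% | 0/20 | 4/70 = 5.7% |
| 10% / 40% | 7 | 25 | 7/45 = 15.6% | 0/25 | 7/70 = 10.0% |
| 15% / 50% | 10 | 30 | 10/40 = 25.0% | 0/30 | 10/70 = 14.3% |

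The zero in *increased* does not depend on the assumptions.

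**4. An AE example.** Suppose 7 stop early, 3 of them for AEs, and 19 of the other 63 switch. AE discontinuation before Week 12 then reads 3/51 = 5.9% against 0/19, while the arm's rate is 3/70 = 4.3%.

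**5. What the mixing does to a subject count.** Person-time is not the share of events, so take an event with probability 5% per 12 weeks on placebo and 10% on drug, independent between periods and with no dropout. *Placebo switched* shows 1 − 0.95 × 0.90 = 14.5% over 24 weeks, and *100 mg continued* shows 1 − 0.90² = 19.0%. Reverse the two probabilities and the figures are 14.5% and 1 − 0.95² = 9.75%. The distortion can go either way.

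**6. Which displays are affected.**
- *Affected:* full-24-weeks AE columns and total; the region, gender and age AE tables, which in Chapter 2 exist for 24 weeks only; whole-study worst-case laboratory and vital-sign summaries; and the 50 mg split, including its first-12-weeks version.
- *Mislabelled only:* the *placebo switched* column in the first-12-weeks split. It is simply the whole placebo arm.
- *Not affected:* all Chapter 1 tables; and the second-12-weeks AE tables, which hold no placebo treatment time and, by 12.1.5, no early stoppers in the denominator.

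**7. Group wording.** SAP 2.1.2 lists five groups including placebo switchers, and the laboratory section (12.2.11) speaks of five adapted groups. SAP 12.3.7 and 12.4.7 instead describe a focus on GLPG0634 use in both periods, which placebo switchers do not meet. The descriptions do not match.

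**The case against.** Much of the defence stands. Chapter 1 already reports AEs, laboratory data, ECG and vital signs to Week 12 by randomised arm, with a GLPG0634-only total for these safety tables. In the example above, Table 14.3.1.13 would show 3/70, and Table 14.1.1.7 gives termination reasons by arm. The five-column tables come in addition to these. A 50 mg subject who stopped early took only 50 mg, so filing the events under 50 mg follows exposure. Any display by treatment sequence conditions on reaching Week 12, and separate columns for early stoppers would not remove that. All of this is prespecified and descriptive.

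The defence does not cover placebo subjects shown under a 100 mg label, the 24-week-only subgroup tables, or the first-12-weeks table that still splits the 50 mg arm by what happened later.

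Three stronger readings are tempting but not supported:

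- *All differences between the two 50 mg columns come from the allocation rule.* They do not: selection on Week 12 response and the dose change itself also contribute.
- *The 24-week total contradicts the SAP's reason for a GLPG0634-only total.* That reason (6.3.2) is easier comparison with placebo. SAP 2.4.2 openly limits that total to data up to Week 12, the 24-week tables have no placebo-only column, and nothing calls the 24-week total a GLPG0634 incidence.
- *Placebo switchers' on-drug ECGs will appear in no table.* A literal reading of 12.3.7 would imply this, since SAP 4.5.3 plans no separate second-period ECG or vital-sign tables. But 12.3.7 and 12.4.7 specify the Safety population, 4.5.2 shows switches as separate arms, and 6.1.3 presents the actual treatments of re-randomised placebo subjects. Exclusion is probably not intended.

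**Conclusion.** The point holds for the 24-week safety displays only. The two 50 mg columns cannot be compared for early discontinuations, nor cleanly for early AEs, because early stoppers can appear in only one of them. On assumed rates, 8–25% of *50 mg continued* never continued. The *placebo switched* column is half placebo time and the all-groups total one-eighth with no dropout, and little more with 5–15% dropout. These are shares of exposure; their effect on AE percentages depends on event rates the documents do not give.

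No primary or inferential result is touched, and the Week 12 safety comparison is sound. The ECG and vital-sign wording is an inconsistency to resolve, not evidence that subjects are left out. The change is worthwhile because it is cheap and these tables will be read for longer-term safety.

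**What to change.** 1. In SAP 2.1.2, show subjects who stopped before Week 12 separately (*placebo, stopped before Week 12* and *50 mg, stopped before Week 12*). Keep 50 mg as randomised, in one column, for every first-12-weeks display. The second step is needed because separate columns alone leave the split conditional on Week 12.
2. In 2.4.2, add to the 24-week tables a total limited to time on GLPG0634, counting placebo switchers from their first GLPG0634 dose, ideally with exposure-adjusted rates. Apply it to the region, gender and age AE tables and to the whole-study worst-case summaries too.
3. In 12.3.7 and 12.4.7, state that all five groups of 2.1.2, placebo switchers included, are tabulated. Section 12.1.7 refers to section 2.4 for the five groups; point it to 2.1.2, where they are listed.

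The cost is a grouping variable, revised table shells and some programming, with no new data. The downside is a few extra columns with small numbers (about 7 subjects each at 10% dropout).

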2.2. FURTHER ANALYSIS POPULATIONS

2.2.1. All Screened Subjects Population

All subjects who signed an informed consent form.

2.2.2. All Randomized Population

All subjects randomized into the study.

2.3. HANDLING OF UNBLINDED SUBJECTS

2.3.1. Safety population

In case a particular subject would be unblinded (e.g., in case of an SAE), all safety data of this subject recorded in the database will still be included in the safety analysis.

2.3.2. Intent to Treat Population

In case a particular subject would be unblinded (e.g., in case of an SAE), all efficacy data of this subject up to the point of unblinding will still be included in the ITT efficacy analysis. Recorded efficacy data from the moment of unblinding onwards will be disqualified from the analysis. Such data will still be part of the listings, but will be labeled as use=no. Missing data after the moment of unblinding will be imputed using the same rules as used for other subjects.

2.3.3. Per Protocol Population

In case a particular subject would be unblinded (e.g., in case of an SAE), all efficacy data of this subject up to the point of unblinding will still qualify for the per-protocol efficacy analysis selection according to the above rule of excluding critical protocol deviations. Recorded efficacy data from the moment of unblinding onwards will be disqualified from the analysis. Such data will still be part of the listings, but will be labeled as use=no. Missing data after the moment of unblinding will be imputed using the same rules as used for other subjects.

2.4. TREATMENT GROUPS

2.4.1. Randomized versus Actual Treatment

For efficacy parameters, the treatment group as assigned by the randomization will be used in the analysis (i.e., as-randomized analysis, considered closest to a worst-case intention-to-treat principle).

For safety parameters, the treatment that was actually used by the subject will be applied in the analysis (i.e., as-treated analysis, considered the fairest worst-case method to allocate potential safety problems to the treatment that was actually used). Such an as-treated analysis will only be done in case more than 20% of the actually used study drug was different than planned and is in a higher dose than planned. If the subject uses less than 20% of incorrect kits or the incorrect kit is a lower dose, then an as-randomized analysis will be applied. The

“20%” mentioned here is over the related study period: period 1 only, or full periods 1+2 combined, or period 2 only (for AE), depending on the analysis chapter.

During the second part of the study: if the subject passed the re-randomization visit (Week 12) but it is unknown whether the subject actually used any study drug during the second part of the study, then it is assumed that the subject used at least one dose of study drug during the second part. If the subject passed the re-randomization visit and it is known that the subject did not take any study drug during the second part of the study, then the re-randomization will be ignored and the subject will only have a study part 1 in the analysis.

Differences between as-treated and as-randomized will be flagged in the listing on subject allocation.

2.4.2. Totals across Groups

A total across all groups will be presented for the General (subject disposition, demographics, etc) part of the analysis. For the Safety parts of the analysis, a total across all GLPG0634 groups will be presented for data up to and including Week 12, and for data after Week 12 or data across the entire 24 weeks of the study a total across all groups will be presented. No totals will be presented for PD or Efficacy. Totals will only be shown on tables, but not on listings or figures.

3. ANALYSIS PERIODS AND ANALYSIS TIME POINTS

3.1. RELATIVE NUMBER OF DAYS

The relative day (DY) is calculated as follows:

= Visit date – reference date + 1 day, when the visit date is on or after the reference date

= Visit date – reference date, when the visit date is before the reference date.

The reference date in the study is the first study medication intake date, which by definition has DY=1. There is no DY=0.

3.2. ANALYSIS PERIODS FOR NON-VISIT DATA

These analysis periods are to be used for allocation of adverse events and concomitant medications into periods.

Analysis period	Period start date	Period end date
Screening	Date of signing the initial ICF.	First study drug administration date – 1 day.
First 12 weeks	First study drug administration date.	Date of the W12 visit.
Second 12 weeks	Date of the W12 visit + 1 day.	Max (trial termination date ; date of last dose + 30 days).
Full 24 weeks	First study drug administration date.	Max (trial termination date ; date of last dose + 30 days).

The trial termination date is the date of last contact with the subject, as recorded in the eCRF.

Note that the last analysis period in case of early termination will always be ended by: *Maximum (trial termination date ; date of last dose + 30 days)*. In case the subject rolls over to DARWIN3, the trial termination date will be used (no 30 days will be added since that would be during DARWIN3).

3.3. ALGORITHM OF ALLOCATING VISITS TO TIME WINDOWS

All visits (including early discontinuation visits and unscheduled visits but excluding visits without data) will be placed into time windows according to their relative day (DY) in the study, according to the following allocation table:

Time point label	Target day	Interval lower bound	Interval upper bound
Screening (3)	NA	NA	NA
Baseline (1)	NA	NA	NA
Week 1	8	2	11
Week 2	15	12	21
Week 4	29	22	42
Week 8	57	43	70
Week 12	85	71	98
Week 16	113	99	126
Week 20	141	127	154
Week 24	169	155	182
>Week 24 (2)	NA	183	+∞
Follow-up (3)	7-10 days after last visit	NA	NA

(NA = not applicable).

Notes:

- (1) The actual baseline reference value will be determined per parameter as the last available pre-dosing data point, so might differ from this “baseline” visit interval. There will be only one baseline time point in this study: the last nonmissing value prior to first dosing of study drug.
- (2) Visits falling really late in the study (relative day > 182; excluding the follow-up visit) will be allocated to a “>Week 24” interval, and will not be shown in tables nor figures, but will only be listed.
- (3) For the screening and follow-up visits, no time window is defined. The visit as recorded in the eCRF will be used. Follow-up visits of subjects who discontinue the study prior to the Week 12 re-randomization will be shown separately as well in the tables that present the first part of the study only. For tables that present the study as a whole, all follow-up visits will be shown.

Tables, figures and listings will present the time points, not the visits.

For ECGs, a different method will be used. See section 12.3 for the details.

